7.8 Next-day residual effect

Coding sub-test[©]

The Coding sub-test[©] is a measure of attention, perceptual speed, motor speed, visual scanning and memory. The total Coding sub-test[©] score is the number of correct symbols entered.

The change from baseline (mean of the two PSG morning assessments at Visit 3, run-in period) to Month 1 and Month 3 (mean of the two PSG morning assessments at Visit 6 and Visit 8, respectively), and Run-out period (Visit 9) in total Coding sub-test[©] score will be summarized. Observed values will also be summarized.

Sheehan Disability Scale[©]

The Sheehan Disability Scale[©] (SDS[©]) consists of three questions on impairment of work, social life, and family life / home responsibilities each on a 10-point scale. The three items will be summed into a single dimensional measure of global functional impairment that ranges from 0 (unimpaired) to 30 (highly impaired). Number of days lost (school, work or normal daily responsibilities) and number of days underproductive (school, work or normal daily responsibilities) are also collected.

The change from baseline (mean of the two PSG morning assessments at Visit 3, run-in period) to Month 1 and Month 3 (mean of the two PSG morning assessments at Visit 6 and

Visit 8, respectively), and Run-out period (Visit 9) in each SDS[®] item (impairment of work, social life, family life / home responsibilities, number of days lost and number of days underproductive) and Total score will be summarized. The Total score will be calculated only for subjects with all the three items available: impairment of work, social life and family life / home responsibilities. Observed values will also be summarized.

Visual analog scales

The morning VAS consists of three questions: quality of subjects' sleep, depth of sleep and sleepiness in the morning. The evening VAS consists of two questions: daytime alertness and ability to function. The VAS scores are collected in the sleep diary and answered on a continuous bipolar (or unipolar for sleepiness in the morning) scale ranging from 0 to 100 points; for all questions, a higher score reflects a better outcome.

The change from baseline^a (Visit 3) to Month 1^b and Month 3^c in morning sleepiness VAS score will be summarized. Observed values will also be summarized.

^a Baseline is the mean value based on the screening sleep diary entries performed at home in the 7 days immediately preceding the first PSG at Visit 3.

^b 'Month 1' is the mean value based on the sleep diary entries performed at home in the 7 days immediately preceding the first PSG at Visit 6.

^c 'Month 3' is the mean value based on the sleep diary entries performed at home in the 7 days immediately preceding the first PSG at Visit 8.

Neurological examination

The time from treatment until the subject is considered safe to leave the center the next day will be summarized for each scheduled PSG visit.

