3.1.1.3 Safety follow-up phase

The **safety follow-up phase** starts after EODBT. It consists of a single-blind placebo Run-out period of 7 days and a Safety follow-up period.

The **Run-out period** starts in the evening of Visit 9. Visit 9 consists of one PSG night on single-blind placebo treatment. Visit 9 is followed by 6 days at home with single-blind placebo treatment. The eDiary is completed every day during the Run-out period. The end of the Run-out period (End-of-Treatment [EOT]) is reached after all visit assessments have been performed at Visit 10.

The **Safety follow-up period** starts after EOT and ends 30 days after last dose of DB study treatment intake for subjects that are not enrolled in the ID-078A303 extension study.

Subjects who complete DB study treatment and the Run-out period are eligible to enter the ID-078A303 extension study (if approved by the national health authorities and local Independent Ethics Committees / Institutional Review Boards [IECs/IRBs]). For these subjects, the Safety follow-up period ends at the date of enrolment into ID-078A303.

[figure not shown]
End-of-Study (EOS) for an individual subject is defined as the date of the 30-day follow-up telephone call (Visit 11, Day 115) or the date of enrollment into the ID-078A303 extension study. If a subject is prematurely discontinued from study treatment, EOS is performed as planned on Day 115. If a subject withdraws consent and does not wish to

participate in the study any longer, EOS is the date of consent withdrawal for this subject. If a subject is declared lost to follow-up, EOS is the date of last successful contact for this subject.

The visit schedule and protocol-mandated procedures are performed according to the table of assessments [Table 1] and are described in Section 7.

The overall study design is depicted in [Figure 1].

Figure 1 Study design

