7.2.3.4 Coding sub-test[©]

The Coding sub-test[©], formerly known as Digit Symbol Substitution Test, is a measure of attention, perceptual speed, motor speed, visual scanning and memory.

On a sheet of paper, the subject is given 120 seconds to complete as many substitutions as possible, entering a symbol in numbered boxes according to a key shown on the top of the sheet (9 symbols).

The Coding sub-test[©] is performed at Visit 3, Visit 6, Visit 8 and Visit 9. The number of correct substitutions is recorded as the total Coding sub-test[©] score and collected in the eCRF.

For further details, see [Appendix 4](#).

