The changes from baseline to the treatment withdrawal period (Visit 9, run-out) in objective sleep parameters (WASO, LPS and TST) will be summarized using descriptive statistics.

The changes from baseline (mean value based on the screening sleep diary entries performed at home in the 7 days immediately preceding the first PSG at Visit 3) to the treatment withdrawal period (after PSG night at Visit 9) in subjective sleep parameters (sWASO, sLSO, and sTST) will be summarized using descriptive statistics.

Next-day residual effect

Observed values and changes from baseline to Month 1 and Month 3 in Coding sub-test[®], SDS[®], and VAS scores (mm) assessing morning sleepiness, daytime alertness and daytime ability to function, will be summarized.

C-SSRS[®]

Number (%) of subjects with suicidal ideation, suicidal behavior, and/or self-injurious behavior without suicidal intent based on the C-SSRS[®] during DB treatment will be tabulated.

Shifts from baseline showing any changes in suicidal ideation and suicidal behavior during DB treatment will also be provided. Subjects will be summarized under the worst of the following three categories, shown here in the order from best to worst: 1) No suicidal ideation or behavior, 2) Suicidal ideation only, and 3) Suicidal ideation and behavior.

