	Weekly Average: Mean of the daily domain score over 7 days	Higher score: greater burden of illness
Sleepiness	Daily: Sum of Item 8*, Item 11, Item 12, Item 13	Minimum score: 0 Maximum score: 40
	Weekly Average: Mean of the daily domain score over 7 days	Higher score: greater burden of illness
Total score	Daily: Sum of all domains above	Minimum score: 0 Maximum score: 140
	Weekly Average: Mean of the daily domain score over 7 days	Higher score: greater burden of illness

* Item 1, Item 2, Item 8, Item 10, and Item 14 scores are reverse scored prior to summation.

A plot of the mean change from baseline over time (per week, as defined in Table 7) for sWASO, sLSO and IDSIQ scores (i.e., Total score; Alert/Cognition and Mood domain scores) will be provided together with a summary table.

The same model as for the main analysis, MMRM [Section 6.1.4], will be fitted for these efficacy endpoints. The LS mean for each treatment group will be displayed along with associated standard errors and 95% CIs. For each ACT-541468 dose level comparison with placebo, the placebo-adjusted LS mean will be displayed along with associated standard error, 95% CI and unadjusted two-sided p-value.

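### The Coding sub-test is given seven times and tabulated by arm, but no difference from placebo or confidence interval is pre-specified for it

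*SAP*

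**What the plan says.** Protocol 7.2.3.4 describes a timed paper test in which "the subject is given 120 seconds to complete as many substitutions as possible"; it "is performed at Visit 3, Visit 6, Visit 8 and Visit 9". SAP 7.8 defines baseline as the "mean of the two PSG morning assessments at Visit 3, run-in period", and Month 1 and Month 3 as the "mean of the two PSG morning assessments at Visit 6 and Visit 8, respectively". For the last administration, protocol 3.1.1.3 says that "Visit 9 consists of one PSG night on single-blind placebo treatment".

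The planned analysis is descriptive in both documents. Protocol 10.3.3 summarises "Observed values and changes from baseline to Month 1 and Month 3 in Coding sub-test" along with the other next-day measures. SAP 7.8 adds the run-out visit, summarising change at Month 1, Month 3 "and Run-out period (Visit 9) in total Coding sub-test" score, and also summarises observed values. SAP 1 and 10.2 produce these by treatment group, with columns for 25 mg, 50 mg and placebo. Unless noted otherwise, the statistics are the count, mean, SD, median, quartiles and range. SAP 9.1 adds scatter plots of plasma concentration against the score.

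For efficacy variables outside the alpha-controlled set, SAP 6.2 goes further: "The same model as for the main analysis, MMRM [Section 6.1.4], will be fitted for these efficacy endpoints". It then displays placebo-adjusted LS means with standard errors, 95% confidence intervals and unadjusted p-values.

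**The concern.** Scores on a repeated speeded test may rise with practice whatever the treatment. If they do, change from baseline in an active arm is the sum of a practice gain and any drug effect, and a value near zero or above does not by itself show that the drug leaves no residual impairment. The randomised placebo arm removes a practice gain that is common to all arms, but only when the arms are contrasted.

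Next-day residual effect is a named safety endpoint (protocol 6.5) of a sleep drug taken every evening, and protocol 1.4.1 already judges such effects unlikely on Phase 2 data. Supporting or revising that judgement needs an estimate of the drug effect and a statement of its uncertainty. The plan supplies the ingredients but not the estimate.

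**Working it through.** **Inputs.** 300 subjects per arm, effect size 0.37 and two-sided alpha of 2.5% are from protocol 10.5. The test schedule is from protocol 7.2.3.4 and SAP 7.8. The documents give no SD, relevant difference or practice gain for the Coding score, so results are in units of the SD of its change from baseline.

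1. **The plan's own figure.** For two groups of 300 the standard error of a difference, in SD units, is sqrt(2/300) = 0.0816. At effect size 0.37, 0.37/0.0816 = 4.53. Subtracting the critical value 2.24 gives 2.29, and the power is 98.9%, as stated. For nine independent tests, 0.989^9 = 0.905, which agrees with the stated figure of at least 90%. These figures concern efficacy; the protocol gives none for the Coding sub-test.

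2. **Number of administrations.** 2 (Visit 3) + 2 (Visit 6) + 2 (Visit 8) + 1 (Visit 9) = 7, that is, six repeats after the first. Two precede double-blind drug, four fall in the double-blind period and one follows a placebo night.

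3. **Precision of a dose-placebo difference.**
   - 300 per arm: half-width of the 95% interval = 1.96 × 0.0816 = 0.160 SD.
   - 255 per arm (15% missing, an assumption: 300 × 0.85): standard error sqrt(2/255) = 0.0886; half-width 1.96 × 0.0886 = 0.174 SD.
   - These are before baseline adjustment, which should narrow the interval.

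4. **What impairment could be excluded.** With no true effect, the interval excludes an impairment D with 80% probability when D = (1.96 + 0.84) × SE. That gives 0.229 SD at 300 per arm and 0.248 SD at 255 per arm.

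5. **What the contrast adds (illustration; gain and impairment are assumed).** Impairment is 0.2 SD in the active arm, and the practice gain is equal in all arms.

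| Practice gain (SD) | Placebo change | Active change | Difference (95% interval) |
|---|---|---|---|
| 0.2 | +0.2 | 0.0 | -0.20 (-0.36 to -0.04) |
| 0.4 | +0.4 | +0.2 | -0.20 (-0.36 to -0.04) |
| 0.6 | +0.6 | +0.4 | -0.20 (-0.36 to -0.04) |

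The active arm's own change moves with the assumed gain; the difference and its interval do not. At 300 per arm the interval would exclude zero with probability 0.69 for a true impairment of 0.2 SD and 0.96 for 0.3 SD. These probabilities describe precision and are not a proposal for a formal test.

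**The case against.** The strongest reply is that the comparator is already in the table. Placebo stands beside both doses, so a gap such as +0.2 SD against zero would be visible. The count, mean and SD also let a reader compute a crude difference and interval. This is correct, and it defeats a stronger reading that a reader might take from the plan, namely that practice can hide impairment. That happens only if an active column is read alone. What remains is that the crude comparison would be informal and adjusted for neither baseline nor age group. The concentration scatter plots do not fill the gap, because the PK set excludes placebo (SAP 4.1.6).

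Three further points limit the claim:

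- **Other objective assessments exist.** Gait, tandem walking and the Romberg test are examined to detect residual effects (protocol 7.2.3.10), and SAP 7.8 summarises the time until the subject may safely leave. The Coding sub-test is therefore not the only objective assessment. It is the only scored performance test; the SDS and VAS are self-reported.
- **The plan does not split benefit from harm.** It is tempting to infer that benefits get a controlled estimate and harms do not. However, IDSIQ Sleepiness and Alert/Cognition, where worse daytime function could also appear, get placebo-adjusted estimates (SAP 6.1.4 and 6.2). Many exploratory efficacy variables in SAP 6.3 get summaries only, and safety variables in general are described rather than modelled.
- **Practice is plausible but not documented.** Two administrations are averaged into baseline and may absorb early learning. Appendix 4 is not readable here, so alternate forms or a practice trial cannot be ruled out.

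**Conclusion.** The plan leaves the drug effect on its one scored next-day performance test, and the uncertainty of that effect, to an informal comparison of columns. The gap is a missing pre-specified contrast, not a missing comparator. The planned sample could support an interval of about ±0.16 SD of change (±0.17 SD with 15% missing).

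A half-width of 0.16 SD does not mean that the trial would exclude any impairment larger than that; this follows only if the observed difference is zero or better. The figure to rely on is about 0.23 SD, excluded with 80% probability when there is no true effect.

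The precision figures assume 300 evaluable subjects per arm (255 for the second case) and an SD common to the arms. The illustration also assumes an additive practice gain that is equal across arms. Neither the size of any practice gain nor the use of identical forms can be confirmed from the documents. The point is a cheap improvement.

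**What to change.** In SAP 7.8, add a model of the Section 6.1.4 form for change in total Coding score at Month 1 and Month 3. The terms are baseline score, age group, treatment, visit, treatment by visit and baseline by visit. Report the LS mean difference from placebo with a 95% interval for each dose at each time point, labelled descriptive. Keep the by-arm summaries.

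The model should not be carried over unchanged, because Section 6.1.4 deliberately includes data after treatment discontinuation, whereas residual effect is a question about subjects on drug. Specify the Safety Set, by actual treatment, and on-treatment assessments. After permanent discontinuation, use only assessments within 24 h of the last double-blind intake, as protocol Table 1 footnote 15 already states for Visit 8. SAP 7.1 does not settle this, since its 7-day rule names only laboratory tests, ECG and vital signs.

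The cost is a short SAP paragraph, a data selection step and a further run of the SAP 15.1 code. It needs no new data and leaves the alpha allocation untouched. The downside is a few nominal intervals on a safety variable, which must not be read as formal tests.

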5.1.7.2 Study treatment compliance

Study treatment compliance is based on study treatment accountability. Subjects also report their compliance in the eDiary every morning. Study treatment compliance for the Run-in period, the DB treatment period (Day 1 to EODBT) and the Run-out period will be separately calculated for each of these periods by site personnel using the below formula and entered in the eCRF:

$$\text{Compliance} = \left[\frac{\text{(number of tablets dispensed – number of tablets returned)} / \text{total number of tablets that needs to be taken during the period}^*}{1} \right] \times 100$$

*The period is defined as number of days during which study treatment should be taken as per actual visit dates.

During the DB treatment period (Day 1 to EODBT), compliance is expected to be at least 70%. Compliance values below this will be considered as a protocol deviation which will be reported in the Clinical Trial Management System by the CRA. The investigator must discuss the non-compliance with the subject to clarify the reasons and to take appropriate actions to avoid re-occurrence. This discussion and its outcome must be documented in the source documents.

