5.1.9 Premature discontinuation of study treatment

The decision to prematurely discontinue study treatment may be made by the subject, the investigator, or Idorsia personnel. The main reason for discontinuation must be documented in the eCRF and in the subject's medical charts (e.g., AE, lack of efficacy).

A subject has the right to prematurely discontinue study treatment at any time, without any justification, by withdrawal from study treatment only or by withdrawal from any further participation in the study (i.e., premature withdrawal from the study [see Section 8.2]). Although a subject is not obliged to give his/her reason for prematurely withdrawing from the treatment or the study, it is recommended that the investigator makes a reasonable effort to ascertain the reason(s), while fully respecting the subject's rights.

The investigator must discontinue study treatment for a given subject if, on balance, he/she believes that continued administration would be contrary to the best interests of the subject.

Study-specific criteria for discontinuation of study treatment are described in Section 5.1.10.

A subject who prematurely discontinues study treatment is NOT considered as withdrawn from the study and will be followed up until the planned EOS (Day 115), provided that the subject's consent for this limited participation in the study has not been withdrawn. The subject is recommended to return for safety assessments [see Table 1] within one week of his/her last DB study treatment intake (N.B., next day residual assessments will only be performed if the subjects can be assessed within 24 h of last DB study drug intake). All subjects withdrawn from study treatment are encouraged to follow planned study procedures (e.g., visits, sleep diary and questionnaire completion) until EOS. In this case, the run-out period (including Visit 9 and Visit 10) will not be performed, and subjects will directly enter the follow-up period after Visit 8 (considered as EOT in the event of premature discontinuation). The phone call will be performed as planned 30 days (+ 7 days) later, at Visit 11. This will decrease the amount of missing data which is important from a study integrity perspective. Subjects who prematurely discontinue study treatment or the study for any reason will not be replaced.

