6.5 Safety endpoints

In addition to the standardized collection of AEs, safety data specific to insomnia and its treatment will be assessed as follows:

- Withdrawal effects (physical dependence) upon treatment discontinuation will be assessed based on the changes from last assessment on DB treatment (Visit 8, 2nd morning) to run-out period in the BWSQ total score (Visit 9 and Visit 10), the occurrence of relevant AEs and marked ECG abnormalities.
- Rebound insomnia will be assessed based on objective sleep parameters (WASO, LPS and TST) at Visit 9 as compared to Visit 3. It will also be assessed using subjective sleep parameters (sWASO, sLSO and sTST) from run-out period as compared to baseline.
- Next-day residual effect will be assessed based on changes from baseline (Visit 3) to Month 1 and Month 3 in:
 - Coding sub-test[©]
 - SDS[©]
 - Scores on the VAS (mm)
- SAEs up to 30 days after DB study treatment discontinuation or until enrollment into the extension study.
- TEAEs up to 30 days after DB study treatment discontinuation or until enrollment into the extension study.

- AEs leading to premature discontinuation of the DB study treatment.
- AEs of special interest after adjudication by ISB:
 - narcolepsy-like symptoms (i.e., EDS, cataplexy and complex sleep behavior events including hallucinations/sleep paralysis)
 - suicide/self-injury
- Change from baseline (Visit 3) to Month 1 (Visit 6) and Month 3 (Visit 8) in vital signs (mean of the 2 PSG nights in systolic and diastolic blood pressure [BP] and pulse rate).
- Change from baseline (Visit 1) to Month 3 (Visit 8) in body weight.
- Marked ECG abnormalities on DB study treatment.
- Change from baseline (Visit 3) to Month 3 (Visit 8) and the end of the run-out period (Visit 10) in ECG parameters.
- Marked laboratory abnormalities on DB study treatment.
- Change from baseline (Visit 3) to Month 1 (Visit 6) and Month 3 (Visit 8) in laboratory parameters.
- Occurrence of suicidal ideation and/or behavior on DB study treatment based on C-SSRS[®].

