7 SAFETY VARIABLES AND ANALYSES

7.1 Overview of safety analyses including subgroup analyses

Unless noted otherwise, the SS will be used for tables and listings of safety data.

Safety data described below will be listed.

In the event of permanent study treatment discontinuation, it is recommended to perform the safety assessments of Visit 8 within 7 days of the last DB study treatment intake. Although some subjects may be considered as being off study treatment, the time from the

last DB study treatment intake to the Visit 8 assessments is expected to be short. Therefore, for subjects who prematurely discontinue treatment, the safety data (laboratory tests, ECG, vital signs) measured within 7 days of the last DB study treatment intake will be included as being taken during DB study treatment. A subject who prematurely discontinues treatment may continue the planned study visits until EOS, without the run-out period. Therefore, for subjects who prematurely discontinue treatment, the safety data (laboratory tests, ECG, vital signs) measured more than 7 days from the last DB study treatment intake will be excluded from analyses.

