12.5 Change from baseline

The change from baseline is defined as post-baseline value (any assessment performed after baseline and up to EOS) minus baseline value. A positive number indicates an increase as compared to baseline.

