12.8 Time window definitions for calculating subjective endpoints

The meaning of the first PSG end date and the last PSG end date at a given visit (Visit 3, Visit 6 and Visit 8) are shown in [Table 6](#).

Table 6 Meaning of the first and last PSG end date at Visits 3, 6 and 8

Visit 3, Visit 6 and Visit 8			
First PSG		Last PSG	
Start date (evening)	End date (morning)	Start date (evening)	End date (morning)

Values falling in the following time windows will be used to calculate weekly averages for the subjective endpoints; values from PSG night will not be included:

Screening: the 7 consecutive days immediately preceding the Run-in single-blind placebo treatment start date but after PSG end date at Visit 1 (morning) (i.e., 7-day window = [Max. (Run-in single-blind placebo treatment start date – 7 days; PSG end date at Visit 1 [morning]); Run-in single-blind placebo treatment start date – 1 day]).

Baseline (Run-in period): the 7 consecutive days immediately preceding the first PSG at Visit 3, but after Run-in single-blind placebo treatment start date (i.e., 7-day window = [Max. (End date of first PSG at Visit 3 – 7 days; Run-in single-blind placebo treatment start date); End date of first PSG at Visit 3 – 1 day]). The time window for Baseline may be less than 7 days. Baseline will be missing for any subjects without a PSG at Visit 3.

Month 1: the 7 consecutive days immediately preceding the first PSG at Visit 6 (i.e., 7-day window = [End date of first PSG at Visit 6 – 7 days; End date of first PSG at Visit 6 – 1 day]). For subjects missing PSG at Visit 6, the 7-day window = [Study day 23; Study day 29].

Month 3: the 7 consecutive days immediately preceding the first PSG morning at (Visit 8 i.e., 7-day window = [End date of first PSG at Visit 8 – 7 days; End date of first PSG at

Visit 8 – 1 day]). For subjects missing PSG at Visit 8, the 7-day window = [Study day 79; Study day 85].

Run-out: the 7 consecutive days immediately following the PSG morning at Visit 9 (i.e., 7-day window = [Date of PSG morning at Visit 9 + 1 day; Min. (Date of PSG morning at Visit 9 + 7 days; Visit 10 date)]). For subjects missing PSG at V9, the 7-day window = [Treatment withdrawal period start date; Min. (Treatment withdrawal period start date + 6 days; Visit 10 date)].

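### The morning-sleepiness VAS, a next-day residual-effect measure, is averaged over home mornings whether or not a dose preceded them; an on-dose mean should stand beside it

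*SAP*

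**What the plan says.** Protocol 6.5 introduces the endpoint with "Next-day residual effect will be assessed based on changes from baseline (Visit 3) to Month 1 and Month 3 in" and then lists the Coding sub-test, the SDS and the VAS scores. SAP 13.3 moves the other VAS items to efficacy, so morning sleepiness is the one VAS item left as a safety variable.

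SAP 7.8 takes its Month 1 value as the "mean value based on the sleep diary entries performed at home in the 7 days immediately preceding the first PSG at Visit 6", with a parallel definition for Month 3 and Visit 8. SAP 12.8 gives the general rule: "Values falling in the following time windows will be used to calculate weekly averages for the subjective endpoints". The only values it removes are those from PSG nights. SAP 12.5 counts as post-baseline "any assessment performed after baseline and up to EOS", and SAP 10.1 accepts two diary days for a weekly mean.

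Two provisions deal with data collected off drug. Under SAP 7.1, for subjects who stop early, "the safety data (laboratory tests, ECG, vital signs) measured more than 7 days from the last DB study treatment intake will be excluded" from the analyses. Under protocol 5.1.9, after premature discontinuation, "next day residual assessments will only be performed if the subjects can be assessed within 24 h of last DB study drug intake". The same section encourages subjects who have stopped to continue visits and the sleep diary until end of study.

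**The concern.** A residual effect is what a dose leaves behind the next morning, so a morning with no dose the evening before carries no information about it. The VAS mean nevertheless takes such mornings in and reports them under the subject's treatment arm. Two kinds of subject contribute them: those who have stopped treatment for good and still fill in the diary, and those on treatment who miss or interrupt doses at home.

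The Coding sub-test and SDS come from PSG mornings, when subjects still on treatment have been dosed on site. For them, the missed-dose problem is specific to the VAS. At stake is whether the by-arm table of morning sleepiness measures what protocol 6.5 says it measures.

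**Working it through.** **1. Is there any dosing condition?** Taking the provisions in turn:

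| Provision | Does it remove drug-free VAS mornings? |
|---|---|
| SAP 7.8 window definitions | No; all home entries in the 7 days |
| SAP 12.8 windows | No; only PSG-night values are dropped |
| SAP 12.8 fallback if the visit PSG is missing | No; fixed Study days 23–29 or 79–85 |
| SAP 10.1 minimum of two days | No; both days may be drug-free |
| SAP 7.1 exclusion beyond 7 days off drug | No; names laboratory tests, ECG and vital signs |
| Protocol 5.1.9 and Table 1 footnote 15 (24 h) | No; concerns when a residual assessment is performed after permanent discontinuation, in Table 1 the Visit 8 one |

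**2. One subject.** Last dose on Day 10, diary continued, first Visit 6 PSG ending on Day 28 (Table 1 target). The Month 1 window is Day 28 − 7 to Day 28 − 1, that is Days 21–27. These days fall 11 to 17 days after the last dose. All seven mornings are drug-free and all enter the active-arm mean, although a laboratory value from those days would be excluded by SAP 7.1. For a subject still on treatment, one missed dose makes 1/7 = 14% of the weekly mean drug-free, and two make 2/7 = 29%.

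**3. Share of mornings in an arm.** The documents give no figure for the VAS. The nearest is the Phase 2 stopping rate in SAP 6.1.4: 14/356 = 3.9% in one month, which reproduces. Let s be the share who stopped before the window and still keep the diary, and m the share of doses missed by the rest. The drug-free share is f = 1 − (1 − s)(1 − m). Assumptions: the monthly stopping rate is constant over three months; every counted stopper is off drug for the whole window; m is 0 or 5%. The value of m has no source in the documents. Two of the 14 withdrew consent, after which no data are collected, so the rows with 12/356 = 3.4% leave them out.

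| Assumption | Month 1 | Month 3 |
|---|---|---|
| No stopper keeps the diary, m = 0 | 0% | 0% |
| s from 12/356, m = 0 | 3.4% | 1 − 0.966³ = 9.8% |
| s from 14/356, m = 0 | 3.9% | 1 − 0.961³ = 11.2% |
| s from 12/356, m = 5% | 1 − 0.966 × 0.95 = 8.2% | 1 − 0.902 × 0.95 = 14.3% |
| s from 14/356, m = 5% | 1 − 0.961 × 0.95 = 8.7% | 1 − 0.888 × 0.95 = 15.7% |

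**4. Effect on the comparison.** Let D be the difference from placebo on mornings after a dose, and r the difference on drug-free mornings. The table then estimates D(1 − f) + r·f. If r = 0, the retained share of D is 1 − f, from 100% down to about 84%. If insomnia returns after stopping, r need not be zero, and the error may go either way. The documents give neither D nor r.

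**The case against.** **The 24-hour rule is not broken.** A reader might infer that the VAS averaging contravenes protocol 5.1.9. It does not. The restriction is written for permanent discontinuation, Table 1 confines it to the Visit 8 residual assessment, and it governs when an assessment is done, not which diary entries are averaged. Isolated missed doses and temporary interruptions lie outside it. Only its intent is at odds with using VAS mornings from subjects who have stopped. This stands.

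**The VAS is not alone.** Table 1 footnote 6 has subjects who stop but stay in the study attend visits as planned, so a subject who stops before Visit 6 could also supply off-drug Coding sub-test and SDS scores there. This stands, and the fix should cover them.

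**Other evidence exists.** SAP 9.1 plots morning-sleepiness VAS against plasma concentration after the second PSG night, when dosing is on site. The ESS, adjudicated excessive daytime sleepiness and adverse events leading to discontinuation are also reported. These lessen the consequence. They do not correct the by-arm VAS summary: the SAP 9.1 plots cover the active arms only and make no comparison with placebo.

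**Including everything is a legitimate estimand.** SAP 6.1.4 adopts a treatment-policy strategy, but for the primary and secondary efficacy endpoints. It does not describe a next-day effect of a dose.

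**Restricting to dosed mornings selects tolerators.** Subjects who stopped because of sleepiness would drop out of the restricted mean. This is a sound objection to replacing the all-entries mean, though not to reporting both.

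**Conclusion.** The point holds in a limited form. The VAS summary offered as a residual-effect measure includes mornings that cannot show one, and no provision in the SAP removes or separates them. The affected share runs from nil to about 10–15% of mornings, resting on a Phase 2 stopping rate carried forward, stoppers keeping the diary, and an assumed 5% of doses missed. SAP 6.1.4 expects a slightly higher rate of intercurrent events in Phase 3 than in Phase 2.

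A reader might go further and infer that the averaging dilutes a harm signal, with subjects who stopped for sleepiness supplying good mornings. The documents do not establish this. Morning sleepiness in insomnia may come from poor sleep as well as from residual drug, so off-drug mornings may be better or worse than dosed ones. The endpoint is summarized descriptively, with no test attached. This is a cheap improvement of low to moderate priority.

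**What to change.** **SAP 7.8:** keep the all-entries mean and add, for all three arms, a post-baseline morning-sleepiness VAS mean restricted to mornings for which the diary records a double-blind dose the evening before. Require at least two such mornings in the window, and give the number of subjects per arm who lose their value through the restriction. Intake after midnight should be assigned to the same night, in line with the convention in SAP 12.2. Baseline is unchanged.

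**SAP 7.1:** extend the statement on off-treatment data to the residual-effect measures in SAP 7.8, namely the VAS and the Visit 6 Coding sub-test and SDS in subjects who have already stopped treatment.

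**Cost:** a few sentences, one filter and one extra table line. No new data are needed: protocol 5.1.2 has the date and time of each home dose entered in the diary, and protocol 5.1.7.2 adds "Subjects also report their compliance in the eDiary every morning". The real downside is that the on-dose line is missing for subjects who stopped before the window, including any who stopped for sleepiness. It should therefore be read together with the all-entries line and the adverse events leading to discontinuation.
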